4.3.3 Exploratory Efficacy Endpoint

The following endpoints will be summarized in subjects with baseline SF ≥ 4 or AP ≥ 2 , and baseline SES-CD, excluding the presence of narrowing component, ≥ 6 (≥ 4 for subjects with initial isolated ileitis).

- Proportion of subjects with average daily SF ≤ 2.8 and not worse than baseline and average daily AP score ≤ 1 and not worse than baseline, by visit.
- Proportion of subjects with decreasing in SES-CD $> 50\%$ from baseline (or for a baseline SES-CD of 4, at least a 2 point reduction from Baseline), by visit.

- Proportion of subjects with $\geq 60\%$ decrease in average daily SF and/or $\geq 35\%$ decrease in average daily AP score and both not worse than baseline, and/or achievement of average daily SF ≤ 2.8 and AP ≤ 1 and both not worse than baseline, by visit.
- Proportion of subjects with SES-CD ulcerated surface subscore of 0 in subjects with SES-CD ulcerated surface subscore ≥ 1 at baseline, by visit.
- Proportion of subjects with SES-CD ≤ 4 and at least a 2 point reduction versus baseline and no subscore greater than 1 in any individual variable, by visit.
- Proportion of subjects who discontinued corticosteroid use for at least 90 days before or at visit and achieved average daily SF ≤ 2.8 and AP ≤ 1 and both not worse than baseline in subjects taking steroids at baseline, by visit.

Note: To summarize discontinuing corticosteroid use for at least 90 days before or at visit in Study M15-989, the concomitant medication records from the feeder Study M15-993 need to be taken into account.

4.3.4 Safety Endpoint

- Vital signs
- Clinical laboratory tests
- Adverse events

4.3.5 Pharmacological Endpoint (Optional)

Pharmacological Endpoint will be analyzed separately and not included in this SAP.

4.4 Sample Size Justification

The sample size is determined by the completion of previous trial Study M15-993/1311.6 and the consenting for the extension.

4.5 Interim Analysis

There will be no formal efficacy interim analysis planned for this study. Since this is an open label study, interim analyses may be performed for publication purpose.

An external independent data monitoring committee (DMC) reviewed safety data throughout the course of the study. A separate DMC charter was prepared outside of the protocol and approved by AbbVie and the DMC members. The DMC is responsible for monitoring safety data, alerting AbbVie to possible safety concerns related to the conduct of the study, and recommending appropriate actions for study conduct and management.

4.6 Multiplicity Testing Procedures for Type-I Error Control

Not applicable.

5.0 Analysis Populations

5.1 Definition of Analysis Populations

5.1.1 Efficacy Populations

Intent-to-Treat Analysis Set

The Intent-to-Treat Analysis Set (ITT) includes all subjects who received at least one dose of risankizumab in the current study.

- The Intent-to-Treat Analysis Set for IV (ITT_IV) includes all subjects who received at least one dose of risankizumab IV in the current study.
- The Intent-to-Treat Analysis Set for SC (ITT_SC) includes all subjects who received at least one dose of risankizumab SC in the current study.

The ITT population will primarily be used for all efficacy analyses. Any by-period analyses on IV (or SC treated population) will be based on ITT IV set (or ITT SC set).

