3. DESCRIPTION OF DESIGN AND TRIAL POPULATION

3.1 OVERALL TRIAL DESIGN AND PLAN

This open label long term extension trial investigates the long term safety and efficacy of BI 655066/ABBV-066 (risankizumab). Approximately 60 patients who meet the entry criteria are planned for inclusion in this trial, rolling over from preceding trial 1311.6. The treatment will be open label.

The treatment period will be 204 ([Flow chart 1](#)), 206 ([Flow chart 2](#)) or 216 ([Flow chart 3](#)) weeks, followed by a 140 day follow up period.

Patients rolling over from preceding trial 1311.6 will have to complete period 2 or 3 in that trial and either demonstrate a clinical response without remission at Visit E1 or a clinical response or remission at Visit E5 as defined by that protocol (see Figure 3.1:1).

[figure not shown]

Figure 3.1:1 Guideline for roll over of patients from 1311.6 to long term extension study 1311.20/M15-989

All patients directly rolled over from 1311.6 into 1311.20/M15-989 will receive 180 mg BI 655066/ABBV-066 (risankizumab) subcutaneously from visit 2 onwards every

8 weeks, until the EoT visit is performed. Patients who complete this study may elect to continue in M16-000 Sub-Study 3 (Phase 3 open label extension study).

Patients who have completed 1311.6 qualifying for roll-over into 1311.20/M15-989 before availability of this study, can be enrolled depending on their clinical remission or response. If patients were treated between finishing 1311.6 and entering 1311.20/M15-989 with anti-TNF therapy or any biologic agent an 8 weeks or 5 times the half-life (whichever is longer), wash-out period will be needed before administration of first i.v or s.c. study medication. Patients must maintain their best response status (clinical response or remission) post 1311.6. Patients who dropped from 1311.6 with remission must maintain remission or undergo re-induction while responders will have to maintain their response.

- If clinical response or remission (CDAI drop >100 from baseline of 1311.6 or CDAI < 150) was maintained after end of treatment and is confirmed at screening for 1311.20/M15-989, patients can directly be assigned to open label s.c. maintenance treatment with 180 mg every 8 weeks (FLOW CHART 1) (visit window between last IMP dose in 1311.6 and first IMP dose in 1311.20/M15-989 should be at least 8 weeks).

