3.3.1 Main diagnosis for study entry

3.3.2 Inclusion criteria

1. Patients with Crohn's disease, who have successfully completed the preceding trial 1311.6. Successful treatment is defined as:
 - Completion of period 2 in 1311.6 with a clinical response (drop in CDAI from baseline by ≥ 100) but no remission (CDAI < 150) at Visit E1; or
 - Completion of period 3 in 1311.6 with a clinical response (drop in CDAI from baseline by ≥ 100) **and** / or remission (CDAI < 150) at Visit E5; or
 - Completion of period 2 or 3 in 1311.6 per protocol with a clinical response or remission before initiation of 1311.20/M15-989 may roll-over either directly if that response/remission is maintained or through an open-label i.v. re-induction phase if they have lost their previous response/remission.(for more details see Section 3.1)

2. Female patients:
 - a. Women of childbearing potential (not surgically sterilized and between menarche and 1 year postmenopause), that, if sexually active agree to use one of the appropriate medically accepted methods of birth control in addition to the consistent and correct use of a condom from date of screening until 20 weeks after last administration of study medication. Medically accepted methods of contraception are: ethinyl estradiol containing contraceptives, diaphragm with spermicide substance, and intra-uterine-device, or
 - b. Surgically sterilized female patients with documentation of prior hysterectomy, tubal ligation or complete bilateral oophorectomy, or
 - c. Postmenopausal women with postmenopausal is defined as permanent cessation \geq 1 year of previously occurring menses, and
 - d. Negative serum β -Human Chorionic Gonadotrophin (β -HCG) test at screening and urine pregnancy test prior to randomization.
- Male patients:
 - a. Who are documented to be sterile, or
 - b. Who consistently and correctly use effective method of contraception (i.e., condoms) during the study and 20-weeks after last administration of study medication.
3. Be able to adhere to the study visit schedule and other protocol requirements.

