5.2 Definition of Treatment Groups

The treatment groups for efficacy analysis are as below:

During IV period: Risankizumab 600 mg IV

During SC period: Risankizumab 180 mg SC

The treatment groups for safety analysis are as below:

During IV period: Risankizumab 600 mg IV

During SC period: Risankizumab 180 mg SC

During the current study: All Risankizumab

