9.0 Efficacy Analysis

9.1 General Considerations

There is no formal statistical hypothesis test planned. Descriptive analyses will be used to analyze the proportion of participants achieving the efficacy endpoints. The study is designed to gain extensive documentation of safety and efficacy.

9.1.1 Analysis of Efficacy Endpoints by Variable Type**9.1.2 Missing Data Imputation for Efficacy Endpoints**

Missing data imputation will be done only for categorical efficacy variables. For the analysis other than efficacy, no imputation will be done for missing values.

Non-Responder Imputation (NRI)

The NRI approach is used for binary efficacy variables. These variables can take values of 'Achieved' or 'Not Achieved' or may be missing for any reason including discontinuation from study. According to the NRI imputation approach, all missing values will be considered as 'Not Achieved.' If a subject has missing value for a specific visit, the data will be imputed using NRI only for the period which the visit belongs to.

Observed Case (OC)

Observed case analysis will be performed, i.e., missing values will not be imputed. An analysis using only the observed data will be performed as a sensitivity analysis for primary and secondary efficacy endpoints.

Imputation of Missing Dates

For baseline, efficacy, and safety parameters, if the day and/or month are missing, the following conventions will be used to impute the missing dates:

- 01 for missing start day
- End of month for missing end day
- January 1st for missing start month
- December 31st for missing end month

In case of partially missing AE start and stop dates, the dates will be imputed by comparing to first dose date of study medication so that the corresponding AEs will be made treatment-emergent whenever possible. If the start date of an AE is partially

missing and the month is the same as the start date of a new therapy, the AE will be made treatment emergent to the new therapy.

In case of missing or partially missing study drug dosing dates, the dates will not be imputed. Subjects will be treated as not receiving dose on that date.

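### The pooled s.c. remission tables mix gain with loss of remission across entry routes, and re-induction failures have no window for their deciding visit

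*SAP*

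**What the plan says.** - **Set and column.** SAP 5.1.1 defines the s.c. set: "The Intent-to-Treat Analysis Set for SC (ITT_SC) includes all subjects who received at least one dose of risankizumab SC in the current study". The same section assigns s.c.-period analyses to it. SAP 5.2 lists one efficacy group for that period: "During SC period: Risankizumab 180 mg SC".
- **Time axis.** SAP Tables 1 to 5 count days from the first s.c. dose. Flow Charts 1, 2 and 3 are shifted by 4, 6 and 16 weeks to reach a common Week 0.
- **Who is in the set.** Protocol 3.1 requires patients rolling over to "either demonstrate a clinical response without remission at Visit E1 or a clinical response or remission at Visit E5". Protocol 3.3.2 words the E1 condition as response "but no remission (CDAI < 150) at Visit E1". It also admits patients who finished 1311.6 before this study opened. Those who kept their status off drug go straight to s.c. dosing on Flow Chart 1. Those who lost it receive three infusions on Flow Chart 3. They move to s.c. dosing if they regain response or remission, and otherwise have an EoT visit.
- **Planned tables.** SAP 9.3 summarises the secondary endpoints by visit, and SAP 9.4 adds nothing. The only subgroup (SAP 4.3.3 and 9.5) uses symptom and endoscopy scores at the feeder-study baseline. No table is split by entry route or by status at s.c. Week 0.
- **Missing data.** Under NRI (SAP 9.1.2), "the data will be imputed using NRI only for the period which the visit belongs to".
- **Main set.** SAP 5.1.1 also says: "The ITT population will primarily be used for all efficacy analyses". The window tables cover only ITT_SC (Tables 1 to 5) and ITT_IV (Table 6), and Table 6 stops at day 71.

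**The concern.** Protocol 3.2 gives early evidence on durability as part of the purpose of the study. In the pooled remission table, direct E1 entrants can only gain remission from their status at E1, while patients already in remission can only keep or lose it. One percentage per visit adds these movements together. The change-from-baseline tables do not separate them either, because the efficacy baseline is the feeder-study baseline (SAP 6.1) and not entry to this study.

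The second problem is the re-induction outcome. Whether a relapsed patient regains response after three infusions is a result in its own right. As planned, the patients who fail leave before the s.c. table starts, and the visit that decides their outcome falls outside the i.v. table.

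The two mechanisms act differently. Pooling can mask a trend, while leaving out the failures mainly raises the level.

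**Working it through.** The plan has no power or precision figure to reproduce. The study is descriptive, and the planned 60 patients is a feasibility count. The entry mix and the remission rates are not in the documents, so those used below are assumptions.

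**1. Pooling.** Let A be direct E1 entrants, B direct entrants in response or remission (E5 roll-overs and early completers who kept their status), and C re-induced patients who reach s.c. dosing.

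Pooled remission = (nA·pA + nB·pB + nC·pC) / (nA + nB + nC)

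Example with A/B/C = 20/30/5:
- Week 0, with A at 0%, B at 90% and C at 50%: (0 + 27 + 2.5)/55 = 53.6%.
- Later, with A at 40%, B at 63.3% and C at 50%: (8 + 19 + 2.5)/55 = 53.6%.

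The pooled curve is flat while B has lost 26.7 points. With C unchanged, a flat curve needs

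fall in B = nA × gain in A / nB

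| Assumed A/B/C | A gains 20 points | A gains 40 points |
|---|---|---|
| 10/40/5 | 5.0 | 10.0 |
| 15/35/0 | 8.6 | 17.1 |
| 20/30/5 | 13.3 | 26.7 |
| 20/25/10 | 16.0 | 32.0 |

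The hidden fall runs from 5 to 32 points. With B starting at 70-90%, that is 6% (5/90) to 46% (32/70) of B's starting rate.

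**2. Re-induction failures and the denominator.** With N = 60 treated, f failures without an s.c. dose and remission rate p among the rest:

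rate over all treated = p(60 − f)/60, so the excess of the s.c. rate is p·f/60

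- At p = 60% and f = 2, 5, 8, 10, the rate over all treated is 58%, 55%, 52%, 50%.
- Smallest excess: 0.50 × 2/60 = 1.7 points. Largest: 0.70 × 10/60 = 11.7 points.

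**3. The deciding visit.** On Flow Chart 3 the infusions are at Weeks 4, 8 and 12, and s.c. dosing would start at Week 16. SAP Table 6 sets i.v. nominal week = protocol week − 4, so Week 16 is nominal Week 12, or day 1 + 7 × 12 = 85. The protocol window of ±7 days gives days 78 to 92. All of these lie beyond day 71, the last day in Table 6. For a patient who continues, this visit becomes s.c. Week 0. A patient who fails has no first s.c. dose, so the visit has no window on either axis, although SAP 6.4 says its windows leave out no post-baseline measurement.

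**The case against.** The strongest reply is that the durability named in Protocol 3.2 is that of clinical response, not remission. Response is required on every route, so the pooled response curve starts near 100% and leaves little room for gains to offset losses. That stands, and it confines the masking to remission. One caution is that Protocol 3.1 and a Flow Chart 3 footnote judge re-induced patients against the 1311.6 baseline, while Protocol 6.2.2 names entry to this study; those passages must be reconciled.

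Other limits also stand:
- The failures are not lost. They remain in ITT, ITT_IV, SA and SA_IV, and in the All Risankizumab safety column. Using s.c.-treated patients for s.c.-period results is a legitimate choice; counting the failures answers a question about the re-induction strategy.
- A reader might infer that every Flow Chart 1 patient starts at zero remission. That is wrong, because Flow Chart 1 also holds early completers who may have kept remission. Even for direct E1 entrants the rule applies at E1, about four weeks before s.c. Week 0.
- A reader might contrast remission among re-induced patients who reach s.c. dosing with remission among all who were re-induced. No planned table shows the re-induced patients separately, so that contrast does not measure the distortion in the pooled column.
- With about 60 patients and no hypothesis tests, strata will be sparse.

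The statement that ITT is the main efficacy set does not settle the matter. The efficacy groups and visit windows exist only by period, so a by-visit ITT table cannot be produced as the plan is written.

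**Conclusion.** The point holds for clinical remission by visit. A flat pooled s.c. rate cannot be read as maintenance, because it may combine new remissions in E1 entrants with losses elsewhere. Under the assumed mixes the hidden fall is about 5 to 32 points. This takes A at 0% at s.c. Week 0, a gain of 20 to 40 points in A, and no change in C. Leaving out 2 to 10 failures of 60, at s.c. rates of 50-70%, raises the pooled rate by about 2 to 12 points. These are illustrations; the true size depends on a mix that the documents do not give. The missing window at i.v. day 85 follows from the SAP's own figures and needs no assumption.

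The issue affects interpretation, not error rates or power. It does not show that durability of response is obscured. Nor does it show that the s.c. safety column is distorted. The last infusion is about 4 weeks before the first s.c. dose, so roughly 16 of the 20 weeks of the protocol's residual effect period fall in the s.c. period, but nothing in the documents shows an effect on adverse event rates, and the All Risankizumab column avoids the split.

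**What to change.** Keep the pooled column and make these additions:

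1. **SAP 9.3:** tabulate clinical remission by visit, split by remission status at s.c. Week 0, including maintenance among those in remission at Week 0.
2. **SAP 9.3:** show response and remission by entry route as counts: direct E1, direct E5, early completers who kept their status, and re-induced. Define the route explicitly, since the flow chart alone does not identify E1 entrants.
3. **SAP Table 6:** add an end-of-re-induction window (nominal Week 12, day 85) starting at day 72, with a stated upper bound. Report response and remission there on the ITT_IV denominator, with failures as Not Achieved. State that for patients who continue, the same visit also serves as s.c. Week 0.
4. **SAP 5.1.1:** reconcile ITT as the main efficacy set with windows that exist only for ITT_SC and ITT_IV, and name the set used for each by-visit table.
5. **Optional, SAP 10.2:** flag s.c.-period adverse events within 140 days of the last infusion.

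The cost is SAP wording and a few more tables. All the data are already collected and study conduct does not change. The drawback is small strata, which is why counts are preferable to percentages alone.

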5.1.2 Safety Populations

The safety analysis set (SA) consists of all subjects who received at least one dose of risankizumab in the current study. Further define two subsets within SA:

- The Safety Analysis Set for IV (SA_IV) includes all subjects who received at least one dose of risankizumab IV in the current study.
- The Safety Analysis Set for SC (SA_SC) includes all subjects who received at least one dose of risankizumab SC in the current study.

5.2 Definition of Treatment Groups

The treatment groups for efficacy analysis are as below:

During IV period: Risankizumab 600 mg IV

During SC period: Risankizumab 180 mg SC

The treatment groups for safety analysis are as below:

During IV period: Risankizumab 600 mg IV

During SC period: Risankizumab 180 mg SC

During the current study: All Risankizumab

6.0 Analysis Conventions

6.1 Definition of Baseline

Efficacy analysis:

For efficacy analysis, the baseline is defined as the last measurement prior to the first dose of the study drug in the feeder Study M15-993 (1311.6).

Safety analysis:

For safety analyses, the baseline is defined as the last measurement prior to the first dose of risankizumab in the feeder Study M15-993 (1311.6).

Demographics and Baseline Characteristics:

For Demographics and Baseline Characteristics, the data will be from the baseline of the feeder Study M15-993 (1311.6).

6.2 Definition of Final Observation

The final observation for each patient will be defined as the last non-missing post-baseline value collected no more than 140 days after the last dose of the study drug in Study M15-989. Any data collected beyond 140 days after the last dose of study drug in Study M15-989 will not be used for analysis but will be displayed in the data listings.

6.3 Definition of Rx Days

The Rx Day is calculated as the event date minus the date of first dose of study drug plus 1 when the time point of interest is after the date of first dose of study drug, or the event date minus the date of first dose of study drug when the time point of interest is prior to the date of first dose of study drug. It provides a quantitative measure of days between the time point of interest and the first study drug dose date. The day of the first dose of study drug is defined as Rx Day 1, while the day prior to the first study drug dose is defined as Rx Day –1 (there is no Rx Day 0).

6.4 Definition of Visit Windows

Since subjects do not always adhere to the study visit schedule, the following rules will be applied to assign actual visits to protocol-specified visits including early termination visits. For each study visit mentioned in the protocol, a nominal or target day will be selected to represent the corresponding visit along with a window around the target day. Windows will be selected in a non-overlapping fashion so that a date collected on the case

report form (CRF) does not correspond to multiple visit windows. Moreover, windows will not discard any post-baseline measurement recorded on the CRF. If a subject had 2 or more actual visits in one visit window, the visit closest to the target will be used as the study visit for that window. If two visits are equidistant from the target day, then the later visit will be used for reporting.

The visit windows and the target/nominal day for each study visit are shown in the tables below. The visit windows defined below will be based on relative days to either first dose on IV or first dose on SC.

Table 1. Windows for subcutaneous injection period for ITT_SC (SA_SC) population, using for Vital sign, Lab Values, Fistula exam, CDAI, Review patient diary (PRO data).

Nominal Visit Week^d	Lower Bound	Nominal Day	Upper Bound
0	-999	1 ^a	1
8	2	57	85
X ^c	$1 + 7*(X - 4) + 1$	$1 + 7*X$	$1 + 7*(X + 4)$
200	1374	1401	9999 ^b

- a. Day of first dose of study drug for subcutaneous injection.
- b. It is minimum of (the last dose date + 140 days, the first dose date of Study M16-000 sub-Study 3) for the subjects who entered the Study M16-000 sub-Study 3; otherwise it is the last dose date +140 days.
- c. $X = 8*i$, $i = 2, \dots, 24$.
- d. Nominal visit week is a transformation of the protocol-specified week. For the patients' schedule following the Flow Chart 1, nominal visit week = protocol-specified week – 4. For the patients' schedule following the Flow Chart 2, nominal visit week = protocol-specified week – 6. For the patients' schedule following the Flow Chart 3 (only for subcutaneous injection period), nominal visit week = protocol-specified week – 16.

Table 2. Windows for subcutaneous injection period for ITT_SC population, using for CDEIS and SES-CD.

Nominal Visit Week ^c	Lower Bound	Nominal Day	Upper Bound
0	-999	1 ^a	1
48	2	337	533
104	534	729	897
152	898	1065	1233
200	1234	1401	9999 ^b

- a. Day of first dose of study drug for subcutaneous injection.
- b. It is minimum of (the last dose date + 140 days, the first dose date of Study M16-000 sub-Study 3) for the subjects who entered the Study M16-000 sub-Study 3; otherwise it is the last dose date +140 days.
- c. Nominal visit week is a transformation of the protocol-specified week. For the patients' schedule following the Flow Chart 1, nominal visit week = protocol-specified week – 4. For the patients' schedule following the Flow Chart 2, nominal visit week = protocol-specified week – 6. For the patients' schedule following the Flow Chart 3 (only for subcutaneous injection period), nominal visit week = protocol-specified week – 16.

Table 3. Windows for subcutaneous injection period for ITT_SC population, using for IBDQ.

Nominal Visit Week ^d	Lower Bound	Nominal Day	Upper Bound
0	-999	1 ^a	1
24	2	169	253
X ^c	1 + 7*(X - 12) + 1	1 + 7*X	1 + 7*(X + 12)
192	1262	1345	9999 ^b

- a. Day of first dose of study drug for subcutaneous injection.
- b. It is minimum of (the last dose date + 140 days, the first dose date of Study M16-000 sub-Study 3) for the subjects who entered the Study M16-000 sub-Study 3; otherwise it is the last dose date + 140 days.
- c. $X = 24*i$, $i = 2, 3, 4, 5, 6, 7$.
- d. Nominal visit week is a transformation of the protocol-specified week. For the patients' schedule following the Flow Chart 1, nominal visit week = protocol-specified week – 4. For the patients' schedule following the Flow Chart 2, nominal visit week = protocol-specified week – 6. For the patients' schedule following the Flow Chart 3 (only for subcutaneous injection period), nominal visit week = protocol-specified week – 16.

Table 4. Windows for subcutaneous injection period for ITT_SC population, using for Fecal Calprotectin

Nominal Visit Week^d	Lower Bound	Nominal Day	Upper Bound
0	-999 ^e	1 ^a	1
24	2	169	281
X ^c	1 + 7*(X - 16) + 1	1 + 7*X	1 + 7*(X + 16)
184	1178	1289	1345
200	1346	1401	9999 ^b

- a. Day of first dose of study drug for subcutaneous injection.
- b. It is minimum of (the last dose date + 140 days, the first dose date of Study M16-000 sub-Study 3) for the subjects who entered the Study M16-000 sub-Study 3; otherwise it is the last dose date + 140 days.
- c. $X = 24 + 32*i$, $I = 1, 2, 3, 4$.
- d. Nominal visit week is a transformation of the protocol-specified week. For the patients' schedule following the Flow Chart 1, nominal visit week = protocol-specified week - 4. For the patients' schedule following the Flow Chart 2, nominal visit week = protocol-specified week - 6. For the patients' schedule following the Flow Chart 3 (only for subcutaneous injection period), nominal visit week = protocol-specified week - 16.
- e. Since some fecal calprotectin data at screening visit are loaded into the last visit of the feeder Study M15-993, the combined fecal calprotectin data from the feeder Study M15-993 and the current Study M15-989 will be used to derive the value at Week 0.

Table 5. Windows for subcutaneous injection period for ITT_SC population, using for hs-CRP.

Nominal Visit Week ^d	Lower Bound	Nominal Day	Upper Bound
0	-999 ^e	1 ^a	1
8	2	57	113
X ^c	1 + 7*(X - 8) + 1	1 + 7*X	1 + 7*(X + 8)
120	786	841	869
128	870	897	925
136	926	953	985
152	986	1065	1093
160	1094	1121	1177
176	1178	1233	1261
184	1262	1289	1345
200	1346	1401	9999 ^b

- a. Day of first dose of study drug for subcutaneous injection.
- b. It is minimum of (the last dose date + 140 days, the first dose date of Study M16-000 sub-Study 3) for the subjects who entered the Study M16-000 sub-Study 3; otherwise it is the last dose date + 140 days.
- c. $X = 8 + 16*i$, $i = 1, 2, 3, 4, 5, 6$.
- d. Nominal visit week is a transformation of the protocol-specified week. For the patients' schedule following the Flow Chart 1, nominal visit week = protocol-specified week - 4. For the patients' schedule following the Flow Chart 2, nominal visit week = protocol-specified week - 6. For the patients' schedule following the Flow Chart 3 (only for subcutaneous injection period), nominal visit week = protocol-specified week - 16.
- e. Since some hs-CRP data at screening visit are loaded into the last visit of the feeder Study M15-993, the combined hs-CRP data from the feeder Study M15-993 and the current Study M15-989 will be used to derive the value at Week 0.

Table 6. Windows for IV injection period for ITT_IV (SA_IV) population, using for Vital sign Lab Values, Fistula exam, CDAI, Review patient diary (PRO data)

Nominal Visit Week ^b	Lower Bound	Nominal Day	Upper Bound
0	-999	1 ^a	1
4	2	29	43
8	44	57	71

- a. Day of first dose of study drug for IV injection.
- b. Nominal visit week is a transformation of the protocol-specified week. For the patients' schedule following the Flow Chart 3 (only for IV injection period), nominal visit week = protocol-specified week - 4.

6.5**Dealing with Multiple Measurements Collected on the Same Day**

For efficacy related analysis, if multiple measurements for a particular parameter are collected on the same day for the same subject, the average of those measurements will be used in analyses.

For safety related analysis, if multiple measurements are made for a particular laboratory or vital sign parameter on the same day for the same subject, the average of the values will be used in the analyses. For summaries and listings for shift from baseline and potentially significant values, all values will be considered in the analyses.

7.0**Demographics, Baseline Characteristics, Medical History, and Previous and Concomitant Medications****7.1****Demographic and Baseline Characteristics**

The following demographic and baseline characteristics, as measured at baseline of the feeder Study (M15-993), will be summarized.

Demographics

- Gender (Male, Female)
- Race [American Indian/Alaska Native, Asian, Black or African American, Native Hawaiian or Other Pacific Islander, White, Other, Multiple]
- Ethnicity [Hispanic/Latino, Non-Hispanic/Latino]
- Age [years]
- Country

Tobacco/Nicotine and Alcohol Use

- Tobacco/Nicotine Use [currently smokes, ex-smoker, never smoked]

- Alcohol Use [Non-drinker, drinks - no interference, drinks - possible interference]

Vital Signs

- Height [cm]
- Weight [kg]
- Weight by sex
- Weight category (< 60 kg, \geq 60 kg)
- Body mass index [kg/m²] (defined as weight/(height/100)²)
- BMI Category
 - Underweight [< 18.5 kg/m²]
 - Normal [\geq 18.5 and < 25 kg/m²]
 - Overweight [\geq 25 and < 30 kg/m²]
 - Obese [\geq 30 kg/m²]

Patient Reported Outcomes at Baseline

- Inflammatory Bowel Disease Questionnaire (IBDQ)
- Average Daily Stool Frequency
- Average Daily Abdominal Pain
- PRO-2

Other Assessments at Baseline

- CDAI
- SES-CD
- CDEIS
- hs-CRP [mg/L]
- Fecal calprotectin
- TNF antagonist exposure (anti-TNF experienced, anti-TNF naive)

- Frequency distribution of draining fistula
- Baseline corticosteroid use (yes, no)
- Crohn's disease duration [year]
- Crohn's disease location (Colon only, Ileum only, Ileocolonic) based on CDEIS

